### 6.7.5 DXA

In the subset of subjects treated at sites where DXA scans are being done, mean changes from baseline to Week 56 in bone mineral density (BMD) and bone mineral content (BMC)-Z scores will be evaluated. The mean change in BMD and BMC will be summarized descriptively as a continuous variable.

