10.8 DXA (Sub Study)

A bone health sub-study will be conducted at selected sites in approximately 100 subjects (25 each on placebo and mid-dose, and 50 on top-dose) to assess the effect of Qsymia administration on bone health using Dual X-ray Absorptiometry (DXA). DXA scans of the posterior-anterior (PA) spine (lumbar), and total body less head (TBLH) will be performed at baseline and at the end of study or early termination. Equipment and procedures used to obtain DXA data will be standardized as described in a separate document. Sites involved in DXA measurement will be trained on these procedures prior to performing scans on study subjects. Scans will be read at a central facility and the reader will be blinded.

The following enrollment criteria will apply:

- 1) Both male and female will be eligible to participate;
- 2) Subjects with a history of any non-traumatic fracture will not be eligible;
- 3) Subjects with juvenile osteoporosis at baseline will not be eligible; and
- 4) Subjects must meet manufacturer equipment specifications with regard to height and weight limitations.

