### **3.5 DXA (Sub Study)**

A bone health sub-study will be conducted at selected sites in approximately 100 subjects (25 each on placebo and mid-dose, and 50 on top-dose) to assess the effect of VI-0521 administration on bone health using Dual X-ray Absorptiometry (DXA). DXA scans of the posterior-anterior (PA) spine (lumbar), and total body less head (TBLH) will be performed at baseline and at the end of study or early termination. Equipment and procedures used to obtain DXA data will be standardized as described in a separate document. Sites involved in DXA measurement will be trained on these procedures prior to performing scans on study subjects. Scans will be read at a central facility and the reader will be blinded.

The following enrollment criteria will apply:

- 1) Both male and female will be eligible to participate;
- 2) Subjects with a history of any non-traumatic fracture will not be eligible;
- 3) Subjects with juvenile osteoporosis at baseline will not be eligible; and
- 4) Subjects must meet manufacturer equipment specifications with regard to height and weight limitations.

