## 6. Statistical Methods

### 6.1 General Principles

All data processing, summarization and analyses will be performed using SAS Environment / Version 9.3 (or later) of the SAS® statistical software package.

The following principles will be applied to all TFLs unless otherwise stated:

Principle	Value
Significant tests	Two-sided and use a 5% significance level.
Treatment group labels and order presented	Placebo VI-0521 Mid VI-0521 Top
Tables	Data in summary tables presented by treatment group, assessment and visit (where applicable).
Listings	All data collected presented by treatment group, site, subject, and visit (where applicable), unless otherwise specified.
Descriptive summary statistics for continuous variables	Number of observations (N), mean, standard deviation (SD), minimum, median and maximum.
Descriptive summary statistics for categorical variables	Frequency counts and percentages [n (%)].
Denominator for percentages	Number of subjects in the pertinent analysis population, unless stated otherwise in table shells.
Include "Missing" as category	Demographics and Other Baseline Characteristics only
Display for 0 percentages	Blank
Display to one more decimal place than collected value	Mean Median Minimum Maximum
Display to two more decimal places than collected value	Standard Deviation Confidence Interval
Limit of precision for displays	3 decimal places
Date Format	DDMMYYYY

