### 6.7.4 Hand and Wrist X-Ray

Changes of bone age from baseline to Week 56 in hand and wrist X-ray will be evaluated. Differences between treatment groups will be evaluated using methods similar to those used to evaluate other continuous variables.

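### The DXA sub-study is meant to assess the drug's effect on bone, but no placebo-subtracted estimate with a confidence interval is planned

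*SAP*

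**What the plan says.** Protocol 10.8 states the aim of the sub-study as "to assess the effect of Qsymia administration on bone health", and SAP 3.5 repeats it under the compound's code name. Both put the size at about 100 subjects at selected sites: 25 on placebo, 25 on mid-dose and 50 on top-dose. Lumbar spine and total body less head (TBLH) are scanned at baseline and at end of study or early termination.

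SAP 6.7.5 first says that "mean changes from baseline to Week 56 in bone mineral density (BMD) and bone mineral content (BMC)-Z scores will be evaluated", and then that "The mean change in BMD and BMC will be summarized descriptively as a continuous variable". Protocol 12.6.3 has the same plan. SAP 6.1 lists the descriptive statistics for a continuous variable as "Number of observations (N), mean, standard deviation (SD), minimum, median and maximum" and lays summary tables out by treatment group.

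Neither document plans a between-group difference, a model or a confidence interval for DXA.

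Two other safety outcomes in the SAP are treated differently. For bone age, SAP 6.7.4 says: "Differences between treatment groups will be evaluated using methods similar to those used to evaluate other continuous variables". For CANTAB, SAP 6.7.1 plans mixed-model least squares means with standard errors, and a standardised difference between placebo and each dose.

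**The concern.** The effect of a drug on bone is a comparison with placebo. The sub-study has a placebo group drawn from the randomised trial, yet the planned output stops at a mean change for each group.

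Change within an active group does not isolate the drug. SAP 2.2 puts every group on the same 500-calorie/day deficit and lifestyle programme. Protocol 8.4.4 itself says that rapid weight loss from caloric restriction may affect growth whatever the drug does. Z-scores are meant to take out the growth expected for age and sex, but they do not take out a diet effect common to all groups. The comparison with placebo does.

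With about 25 placebo subjects, a table of similar-looking means could be read as showing no effect on bone, and nothing in the planned table would show how large an effect remains compatible with the data. Safety is one of the trial's primary objectives, so the size of that uncertainty should be reported.

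**Working it through.** **What is planned, side by side**

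| Outcome | Planned analysis | Between-group estimate? |
|---|---|---|
| DXA (SAP 6.7.5) | Mean changes evaluated; descriptive summary | None named |
| Bone age (SAP 6.7.4) | Group differences evaluated as for other continuous variables | Yes, but no model or interval named |
| CANTAB (SAP 6.7.1) | Mixed-model least squares means with standard errors; effect size versus placebo | Yes, but no interval named |

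**Figures to reproduce.** The documents give no power, precision target, effect size or SD for the DXA sub-study, so there is no stated figure to check. The calculation below gives the precision that the missing estimate would have.

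**Inputs**
- Scans per group: 25 placebo, 25 mid-dose, 50 top-dose (SAP 3.5).
- Two-sided 5% level, hence 95% intervals (SAP 6.1).
- Scan loss: not given for DXA. The 30% is borrowed from the main-trial sample size (SAP 2.3) as an assumption, and a range of 0 to 40% is shown. SAP 5.2 imputes no missing safety data.
- SD of change in Z-score: not given. Results are therefore in units of that SD, assumed equal across groups.

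**Formula.** Half-width in SD units = t(0.975, n1 + n2 − 2) × √(1/n1 + 1/n2), with no covariate adjustment.

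**No loss**
- Top-dose vs placebo (50 vs 25): √(1/50 + 1/25) = 0.245; multiplied by t on 73 df, the half-width is 0.488.
- Mid-dose vs placebo (25 vs 25): √(1/25 + 1/25) = 0.283; multiplied by t on 48 df, it is 0.569.

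**30% loss.** 0.7 × 50 = 35, and 0.7 × 25 = 17.5, rounded down to 17.
- Top-dose vs placebo (35 vs 17): 0.594.
- Mid-dose vs placebo (17 vs 17): 0.699. Using 17.5 without rounding gives 0.588 and 0.688.

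**40% loss** (30 vs 15, and 15 vs 15): 0.638 and 0.748.

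**Reading.** Suppose the observed means were identical in all groups. With every scan obtained, a half-SD deficit would be only just outside the interval for top-dose (0.49) and inside it for mid-dose (0.57). At 30% loss it would be inside both. Adjustment for baseline value and strata would narrow these intervals, by an amount the documents do not allow one to state.

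**The case against.** The strongest reply is that descriptive reporting is a legitimate choice for a safety sub-study of about half the sample. The protocol and SAP agree on it. Laboratory values and vital signs are also descriptive, and SAP 6.7.6 rules out statistical comparison of adverse events. The bone-age and CANTAB sections do not promise a confidence interval either. All of that is correct, so this is not a conflict between documents. But the adverse-event rule covers only adverse events, and the DXA sub-study was created to assess one specific effect.

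A reader might go further and infer that the sub-study cannot answer its own question. The documents do not support that. Placebo will be tabulated beside both doses, and N, mean and SD per group are enough to work out an unadjusted difference and interval by hand. What is lacking is a prespecified, adjusted estimate.

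A reader might also infer that the baseline scan, age and gender go unused. That is not so either. The measure is a change from baseline, and Z-scores by ordinary definition are referenced to age and sex, although the documents do not define the reference used. These variables are absent only as model covariates. The argument that adolescents gain bone anyway therefore has little force for Z-scores. It would apply to raw values, which the second sentence of SAP 6.7.5 may also cover, since it drops the reference to Z-scores.

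Two further limits stand. The half-widths measure the precision of the proposed estimate, not an error in the present plan, and an interval this wide would not reliably detect a half-SD deficit. Its use is to show what has not been excluded. Also, the 30% loss may be too high for scans, because they are scheduled at early termination as well.

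**Conclusion.** The point holds as a gap between the aim and the planned analysis. The sub-study is to assess a drug effect, and the plan neither prespecifies an estimate of it against placebo nor shows its uncertainty. The vague wording about evaluating mean changes does not fill the gap: unlike the bone-age section, it names no difference between groups.

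The estimate would have a 95% half-width of about 0.49 SD of change for top-dose versus placebo and 0.57 SD for mid-dose versus placebo with all planned scans, or about 0.59 and 0.70 SD at an assumed 30% loss. These figures rest on the planned 25/25/50 split, a common SD and no covariate adjustment. Because the documents give no SD for Z-score change, they carry no stated clinical meaning. The efficacy conclusions are not affected.

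**What to change.** In SAP 6.7.5, keep the descriptive table and add, for change in BMD and BMC Z-scores at lumbar spine and at TBLH:

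- top-dose minus placebo and mid-dose minus placebo, each with a 95% confidence interval;
- an ANCOVA with treatment, baseline value, age stratum and gender;
- a statement that this is estimation only, without p-values, so that it makes no claim on the type 1 error plan;
- Week 56 scans as the main analysis, repeated with early-termination scans included. This needs saying because SAP 3.5 schedules scans at either time while SAP 6.7.5 speaks only of Week 56, and mixing them would make length of follow-up differ between subjects.

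Protocol 12.1 allows the SAP to modify or add analyses. It requires a protocol amendment only for major changes to the primary endpoint or its analysis, so none is needed here. The cost is one extra table and its repeat, from data already being collected. The downside is that wide intervals will make the sub-study's limited precision plain.

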### 6.7.6 Adverse Events

All adverse events (AEs) recorded on the eCRF will be coded using the MedDRA dictionary Version 21.1 (or a later version if updated during the study) and classified as either pre-treat AEs or treatment – emergent AEs (TEAEs) as follows:

- Pre-treat AEs are events that start prior to the date of first dose of study treatment.
- TEAEs are events with start date on or after the date and time of first dose of study treatment and up to 28 days after date and time of last dose of study treatment or events with start date and time prior to the date and time of first dose of study treatment whose severity worsens on or after the date and time of first dose of study treatment.

All AE data will be listed by treatment group. Treatment-emergence status will be flagged in the listing. In addition, corresponding listings of serious AEs (SAEs), AEs leading to discontinuation of study treatment and AEs resulting in death will be produced.

Summary tables of TEAEs by treatment group will be produced for the Safety population.

The severity of all AEs is recorded as mild, moderate, or severe. If severity is missing for a TEAE, it will be considered severe only in the overall category in the summary tables.

The relationship between an AE and study treatment is assessed as Related or Not Related by the investigator.

An overview table will summarize the number and percentage of subjects with at least one of the following TEAEs, where subjects with more than one TEAE in a particular category are counted only once in that category:

- Any TEAE
- Any TEAE by severity (mild, moderate, severe)
- Drug-related TEAE
- TEAE leading to dose reduction
- Drug-related TEAE leading to dose reduction
- TEAE leading to study treatment discontinuation
- Treatment-emergent SAE
- Drug-related Treatment-emergent SAE
- Treatment-emergent SAE leading to death;
- Drug-related Treatment-emergent SAE leading to death
- Treatment-emergent SAE leading to treatment discontinuation

The number and percentage of subjects reporting each TEAE will be summarized by System Organ Class (SOC) and Preferred Term (PT) for the Safety population. Tables will be sorted alphabetically by SOC. PTs will be sorted by descending overall total. The following summaries will be produced:

- TEAEs by SOC and PT
- Drug-related TEAEs by SOC and PT
- TEAEs by maximum severity by SOC and PT
- TEAEs related to treatment by maximum severity by SOC and PT
- TEAEs causing discontinuation from treatment by SOC and PT
- TEAEs related to treatment causing discontinuation from treatment by SOC and PT
- SAEs by SOC and PT

In the above summaries, subjects with more than one AE within a particular SOC are counted only once for that SOC. Similarly, subjects with more than one AE within a particular PT are counted only once for that PT. For summaries by maximum severity, subjects with multiple AEs within a particular SOC or PT will be counted under the category of their most severe AE within that SOC or PT.

No statistical comparisons of AEs between treatment groups will be performed.

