11.3 Reporting Period

The reporting period for adverse events begins when the subject provides written informed consent and extends until 28 calendar days after the last day of study participation. All adverse events that occur during this period and are known to the investigator must be reported according to the requirements outlined in this protocol.

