12.6.4 Adverse Events

Adverse events will be coded using a MedDRA coding dictionary. The number and percentage of subjects who reported at least one adverse event in each system organ class and preferred term category, and the total number and percentage of subjects with any AE over all system organ classes will be summarized by treatment group.

Subsets of AEs that are considered serious or required discontinuation of the study medication will be summarized separately and listed by subject.

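### SAP 6.7.6 sorts adverse events into two classes that leave no place for new events starting more than 28 days after last dose, although the protocol collects them and plans counts of subjects with any adverse event

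*SAP*

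**What the plan says.** **Collection.** Protocol 11.3 starts adverse-event reporting at consent, and the period "extends until 28 calendar days after the last day of study participation". It adds: "All adverse events that occur during this period and are known to the investigator must be reported". Protocol 6.0 and 7.3 and SAP 2.2 encourage subjects who stop drug to keep attending visits to Week 56.

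**Planned summary in the protocol.** Protocol 12.6.4 plans "The number and percentage of subjects who reported at least one adverse event in each system organ class and preferred term category", and also that "the total number and percentage of subjects with any AE over all system organ classes will be summarized by treatment group". Neither statement is limited to treatment-emergent events.

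**Classification and tables in the SAP.** Under SAP 6.7.6 all events recorded on the eCRF are "classified as either pre-treat AEs or treatment – emergent AEs (TEAEs) as follows". The first class is defined thus: "Pre-treat AEs are events that start prior to the date of first dose of study treatment". The second covers events starting on or after first dose and "up to 28 days after date and time of last dose of study treatment", together with pre-dose events that worsen after dosing starts. The tables then follow from the second class: "Summary tables of TEAEs by treatment group will be produced for the Safety population". All events are listed by treatment group with a treatment-emergence flag, and serious events and deaths have their own listings. SAP Section 1 names Amendment 2 as a source document. SAP Section 7 declares no changes to the planned analysis.

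**The concern.** The two documents measure 28 days from different points. The protocol counts from last participation and the SAP counts from last dose. They agree for a subject who takes drug to the end, or who leaves the trial on stopping drug. They part for a subject who stops drug permanently and stays, which is what the protocol asks for.

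For that subject the SAP's either/or scheme cannot be applied to every event it claims to classify. A new late event is not pre-treatment and is not treatment-emergent, so it enters no table restricted to treatment-emergent events. Safety is a primary objective, and a by-arm count of deaths or serious events that stops 28 days after last dose can differ from the count over the period in which those events were collected. Pregnancy is one example. Protocol 11.4.3 requires treatment to be discontinued and treats certain outcomes as serious events. Such an outcome may fall more than 28 days after last dose yet still within the reporting period.

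**Working it through.** No sample-size, power or alpha figure is involved, so there is no stated number to reproduce. The check is date arithmetic followed by a comparison of tables.

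**Inputs.** Week 56 is Day 56 × 7 = 392 (Protocol 6.0 and 9.2, counting from Day 0). Both documents use a 28-day tail. Last participation is taken as Day 392 for a subject followed to the end.

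**Formulas.**
- Protocol period ends: last participation day + 28 = 392 + 28 = Day 420.
- SAP new-onset window ends: last dose day + 28.
- Uncovered interval: (last participation + 28) − (last dose + 28) = last participation day − last dose day.

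| Last dose | SAP window ends (day) | Protocol period ends (day) | Uncovered days |
|---|---|---|---|
| Week 4 (Day 28) | 56 | 420 | 364 |
| Week 12 (Day 84) | 112 | 420 | 308 |
| Week 16 (Day 112) | 140 | 420 | 280 |
| Week 28 (Day 196) | 224 | 420 | 196 |
| Week 40 (Day 280) | 308 | 420 | 112 |
| Week 52 (Day 364) | 392 | 420 | 28 |
| Week 56 (Day 392) | 420 | 420 | 0 |

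For the Week 28 stop, 392 − 224 = 168 of the 196 days lie within scheduled follow-up, when Protocol 11.2 has sites ask about events at each visit. The other 28 days are the protocol's tail after participation ends.

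**Where a new event in the uncovered interval goes under SAP 6.7.6.**
- Overview table: excluded. Every row is a treatment-emergent count, including those for serious events and for serious events leading to death.
- Tables by system organ class and preferred term for all, drug-related, by-severity and discontinuation events: excluded, because they are treatment-emergent tables.
- Serious events by system organ class and preferred term: unclear. The entry does not carry the treatment-emergent label, but it sits in a list introduced as summaries of treatment-emergent events.
- Listings: included.

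**Limit of the gap.** It concerns new-onset events only. The clause on worsening of pre-dose events has no upper time limit, so late worsening of a pre-existing event still counts as treatment-emergent.

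**The case against.** The case on the other side has real substance.

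- *A 28-day post-dose window is legitimate.* Agreed, and the fix keeps it. Protocol 11.1 also refers to 28 days after last dose when describing follow-up of related events.
- *Protocol 11.3 is a reporting period, and 12.6.4 sets no analysis window.* True. Read literally, any event would also include those before first dose. Protocol 12.1 lets the SAP modify the plan without an amendment unless the primary endpoint or its analysis changes in a major way. So the SAP may narrow the summary. What stands is that it does so without saying so in Section 7, and with classes that do not cover the collected data.
- *Nothing is lost, because everything is listed.* The data are indeed kept, and no statistical comparison of adverse events is planned, so no test changes. But a listing does not give the by-group numbers and percentages that Protocol 12.6.4 describes.
- *Late serious events may be tabulated anyway.* Possibly, in the one table noted above. Its scope needs to be stated, and it would not cover non-serious events.

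Two stronger readings are tempting and do not hold. A reader might infer that a suicide attempt some weeks after stopping drug would go uncounted. SAP 6.7.3 tabulates every C-SSRS item by group at each visit, and SAP 6.7.2 counts subjects with a positive PHQ-9 question 9. Neither has a treatment-emergent cut-off, and both instruments are scheduled at every visit. Suicidality is therefore partly covered. A reader might also turn the 30% dropout rate in the sample-size section into a share of follow-up lost from the tables. That rate is a power-calculation allowance and does not say how many subjects stop drug and stay. Those who leave on stopping add little or nothing to the gap.

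**Conclusion.** The concern holds in a limited form. Followed exactly, SAP 6.7.6 leaves new-onset events more than 28 days after last dose unclassified. It also keeps them out of the overview table and the treatment-emergent tables by system organ class and preferred term, although the protocol collects these events and plans counts of subjects with any event. They remain in the listings and possibly in one serious-event table.

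Per subject, the uncovered interval runs from 0 days when dosing continues to Week 56, through 196 days for a stop at Week 28, to 364 days for a stop at Week 4. These figures assume a permanent stop and follow-up to Day 392. The documents do not give the share of subjects who will be off drug but still followed, so no trial-wide percentage can be stated. Nor do they show that the arms will differ in this respect. The conclusion rests on the wording of the classes and does not depend on either quantity.

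**What to change.** In SAP 6.7.6:

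1. Keep the treatment-emergent definition and its tables.
2. Add a third class, post-treatment, for events starting more than 28 days after last dose up to the end of the Protocol 11.3 reporting period, and tabulate it by treatment group.
3. Count deaths and serious events by treatment group over the whole reporting period as well as within the treatment-emergent window.
4. State whether the table of serious events by system organ class and preferred term covers all serious events or only treatment-emergent ones.

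In SAP Section 7, record that the main adverse-event tables are narrower than the any-event summary in Protocol 12.6.4.

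The cost is SAP wording and a few extra tables from data already collected. No new assessments and no change to the protocol's collection rules are needed.
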